12.3. Reporting Serious Adverse Events

SAEs will be reported from randomisation up until 20 weeks post randomisation (i.e. 16-week follow-up plus the 4-week window allowed for completion of questionnaires).

In a bid to commit to data minimisation (especially of sensitive category data), we will not respond to or report SAEs for non-randomised participants. Depending on the attrition rate during completion of baseline assessments, the number of individuals who do not convert to randomisation could be significant, and therefore beyond the capacity of the research team to follow-up events. Only randomised participants (i.e. those offered the intervention) will be monitored for safety.

In the event a member of the research team becomes aware of a (potential) SAE, a PWP will endeavour to contact the participant by telephone and/or email to enquire about the safety and well-being of the participant, determine whether a SAE has occurred and offer support as described in Section 12. If a SAE has not occurred, the PWP/coach will document it on the risk log, but no further data will be collected.

In the event of a SAE the PWP or site lead will complete a SAE report form on REDCap Academic to capture key information about the event. This will include:

- Event name (brief term describing the event)
- Reason for being an SAE
- Date of occurrence (estimated if exact date unknown)
- Date research team became aware of event
- Detailed description of the event and any actions taken
- Status of the event (ongoing, resolved, death)
- Intensity (mild, moderate, severe)
- Causality (relationship to the study intervention)
- Name and signature of person assigning causality

If a SAE is categorised as related to the intervention, a statement will appear on the SAE form informing the research team that the event is a Related Unexpected SAE (RUSAE) and must be reported to the Sponsor, DMEC and REC following the expedited timeframe (15 days for the DMEC and REC).

If the SAE is ongoing at the time of the initial report, follow-up report forms will be completed until the event is resolved, the participant has died, or the Sponsor and CI agree that no further follow-up is required. Where possible, efforts will be made to ensure any ongoing SAEs are resolved prior to database lock.

If an event is recorded as an SAE in the first instance but it is later determined that the event did not meet the definition of an SAE, the event will be marked as withdrawn in the REDCap database, but the data will not be removed. There will be no further follow up of such events.

Serious adverse events (SAE) will be reported to the TMG monthly. The Chief Investigator will review aggregate SAE data monthly through receipt of the TMG report and will determine whether there are any safety concerns arising which could have implications for other participants. This will be documented in TMG meeting minutes. If the event was a death, or resulted in death, the Chief Investigator will review the event and determine the potential safety implications for other study participants within one week of the event.

SAEs categorised as related to the intervention (RUSAEs) will be reported to the DMEC and the Research Ethics Committee who provided favourable opinion for the study within 15 days of the research team becoming aware of the event.

Aggregate SAE data will be reported to the DMEC and TSC biannually as part of their oversight of the study.

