Similar standard operating procedures including risk assessment, signposting to relevant sources of help and bringing in relevant clinically qualified members of the team (clinical psychologists, psychological wellbeing practitioners in UK), will be used by research staff if participants report worsening of symptoms or suicidality during interviews or contacts with research staff.

The study has been designed in collaboration with a Lived Experience Advisory Panel (LEAP) who have advised on all aspects of the intervention.

A detailed risk assessment has been completed by Exeter Clinical Trials Unit and will be maintained throughout the study.

Information about possible benefits and risks of participation will be described in the Participant Information Sheet (PIS).

USA-specific detail

The study will be reviewed and approved by an Institutional Review Board at UCLA, USA.

Digital CBT is widely available for patients and is frequently incorporated into research studies in the USA.

Coaches, supervised by a licensed clinician, will support participants recruited in the USA.

For participants recruited in the USA, automated signposting to support services will be tailored to services specific to the local study population in the USA. USA-based participants will be students at the Imperial Valley Community College (IVC), so services will include the student support services already available through the College.

During screening, if individuals indicate the exclusion criteria of active suicidality, severe PTSD or diagnosis of bipolar disorder, substance abuse or psychosis they will be provided with contact information for the college health centre counselling services, as well as community emergency resources.

If, during the study, participants indicate suicidality on self-report assessments, they will be provided with information about community and emergency resources. Additionally, study staff may provide participant contact information to the IVC Behavioral Intervention Team (BIT) for their team to conduct independent follow up with students. Participants will be informed of this potential for information sharing in the informed consent signed before study enrollment.

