If a participant discloses suicidality during an encounter with study staff, study staff will provide the participant with information about community and emergency resources, and report to the Coaching Supervisor. Additionally, study staff may provide participant contact information to the IVC Behavioral Intervention Team (BIT) for their team to conduct independent follow up with students.

If during the course of the study a participant's responses to surveys indicate a significant worsening of symptoms, they will be provided with contact information for the IVC health center, as well as community and emergency resources. This is defined as a deterioration of movement across two or more score categories on the GAD7 or PHQ-9 from baseline to 16-weeks or from baseline to 52-weeks follow-up.

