7.2. Exclusion criteria

Participants who self-report meeting ANY of the following criteria at time of recruitment will be excluded from study participation:

1. Concurrent psychotherapy
2. Current self-reported diagnosis of any of the following conditions, including receiving or waiting for treatment:
 - Alcohol abuse/dependence
 - Substance abuse/dependence
3. Self-reported diagnosis of current or history of bipolar disorder or psychosis at any time
4. Taking antidepressants or anxiolytic medications at a stable dose for less than six weeks
5. Severe post-traumatic stress disorder (PTSD, assessed as a score of 17 or higher in total for the first six questions AND a score of 2 or higher on the seventh question of the adapted International Trauma Questionnaire⁵⁸; ITQ)
6. Suicidal thoughts and self-harm assessed by a combination of PHQ-9³⁸ **question 9** score of 1 or higher and a yes to question R1a and/or R1B, and a yes to either question R2 and/or R3 (detailed below):
 - *R1a = In the last 2 weeks have you been experiencing regular thoughts about suicide?*
 - *R1b = In the last 2 weeks have you been experiencing regular thoughts about self-harm?*
 - *R2 = In the last 2 weeks have you had any intention to hurt or kill yourself?*
 - *R3 = In the last 2 weeks have you made any plans to harm yourself or end your life?*

People who are excluded from the study will be provided with information signposting them to relevant advice or support. If a person indicates that they have intention to, or made plans to, hurt or kill themselves in the past 2 weeks the screening form will enable the person to volunteer their contact details and GP details if they would like to receive a phone call from a member of the research team, and potentially be referred to their GP.

The PWPs will follow a separate risk management protocol to assess and support any individuals who are identified as being at risk during the study.

USA-specific detail

For participants recruited in the USA, automated signposting to support services will be tailored to services specific to the local study population in the USA.

During screening, if individuals endorse the exclusion criteria of active suicidality, severe PTSD or diagnosis of bipolar disorder, substance abuse or psychosis they will be provided with contact information for the college health center counseling services, as well as community emergency resources.

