SAEs which are categorised as related to the intervention (Related Unexpected SAE (RUSAЕ)) will be reported to the Sponsor using a SAE template report form produced by ExeCTU. ExeCTU will report RUSAЕs to the Sponsor as soon as reasonably practicable after becoming aware of the event, taking into account that the Sponsor must report the event to the REC within 15 calendar days.

SAEs may be detected by the research team via interaction with the participant and some will be detected by data submitted by participants on the assessment forms in which case, it may not always be possible to obtain full details of an event before submitting the initial report. The research team (typically PWP) will endeavour to make contact with the participant by email and telephone to obtain as much detail as possible and signpost to relevant support if appropriate. All attempted and actual contacts will be documented on a contact log.

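### Read literally, Section 12.3's words on not responding to SAEs conflict with Section 2 in one narrow case: a suicide attempt disclosed to staff after consent but before randomisation

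*Protocol*

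**What the plan says.** Section 12.3 sets SAE reporting to run from randomisation to 20 weeks. Citing data minimisation and limited capacity for follow-up, it then says of people who have consented but are not randomised that "we will not respond to or report SAEs for non-randomised participants". The paragraph closes: "Only randomised participants (i.e. those offered the intervention) will be monitored for safety".

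The same section describes what happens when staff learn of a possible SAE: "a PWP will endeavour to contact the participant by telephone and/or email to enquire about the safety and well-being of the participant", with an offer of support. Section 12.1 says the contact is also meant "to obtain as much detail as possible and signpost to relevant support if appropriate". Its definitions table counts suicide attempt, new or increased self-harm, and referral to crisis care among SAEs.

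Section 2 describes procedures of risk assessment, signposting and clinical input that "will be used by research staff if participants report worsening of symptoms or suicidality during interviews or contacts with research staff". Its USA text begins "If a participant discloses suicidality during an encounter with study staff" and goes on to require that staff give details of emergency and community resources and report to the Coaching Supervisor. Neither rule mentions randomisation.

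**The concern.** A protocol may confine SAE data to people who were offered the intervention, and that choice is not questioned. But responding to an event and reporting it are different acts, and Section 12.3 switches off both. Taken at its word, it tells staff to do nothing about an event for which Section 2 prescribes help. No sentence says which rule prevails.

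What is at stake is participant safety. Of the two instructions, the literal one in Section 12.3 is the worse for the participant.

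**Working it through.** No power, rate or sample-size calculation applies. The check sets the texts side by side and then looks at the time window.

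**1. Who is covered.** Sections 8.3 and 11 both use the word participant for people who have consented but are not yet randomised. The Section 2 rules, which are worded for participants, can therefore include them. Section 12.3 names the non-randomised explicitly.

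**2. Which events fall under both rules.** Section 12.3 concerns SAEs; Section 2 concerns suicidality and worsening symptoms.

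| Disclosed before randomisation | SAE under 12.1? | Within Section 2? | Conflict? |
|---|---|---|---|
| Suicidal thoughts, plans or intent only | No | Yes | No |
| Suicide attempt | Yes | Yes | Yes |
| New or increased self-harm | Yes | Less directly, because 12.1 defines it as without intent to end life | Possible |
| Crisis referral or overdose admission | Yes | If suicidality is involved | Possible |
| Serious accident without suicidality | Yes | No | No |

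**3. Whether responding can mean data handling only.** The sentence opens with data minimisation, which favours that reading. Against it, the reason that follows is capacity to follow events up, and in Sections 12.1 and 12.3 the SAE contact itself carries signposting and an offer of support. The wording is therefore not clearly confined to data.

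**4. Whether a blanket refusal looks intended.** Section 7.2 lets people screened out for suicidal intention or plans, who will never be randomised, leave their details "if they would like to receive a phone call from a member of the research team, and potentially be referred to their GP". It also has PWPs follow a risk protocol "to assess and support any individuals who are identified as being at risk during the study". The first provision concerns intention or plans rather than an SAE, but both suggest that a total absence of response is not the aim.

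**5. Whether the situation can arise.** Section 8.3 offers an optional researcher call before randomisation and allows researchers to contact people who have not finished baseline or EMA. Staff contact in this period is therefore planned. The timings are:

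- Eligibility to consent: up to 2 weeks = 14 days (Section 8.2).
- Consent to end of baseline: up to 4 weeks = 28 days, extendable; minimum 10 days (Section 8.3; Table 3, note g).
- PHQ-9 with its linked suicide-risk questions: asked at screening and carried forward as baseline data, not repeated (Section 8.1.1; Table 3).

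The longest normal gap from those questions to randomisation is 14 + 28 = 42 days, before any extension. This shows how long an event could go unasked about. It says nothing about how often one occurs.

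**The case against.** The strongest reply is that both rules can be followed at once. Section 12.3 is about reporting, and the process it describes consists of an outbound PWP contact, a decision on whether an SAE occurred, a form and follow-up reports. A researcher on a baseline call could give all the help in Section 2 and start none of that. The protocol also keeps risk management apart from SAE handling, with separate risk logs and a separate risk protocol. Section 11 confines risk monitoring to those in active follow-up, and Section 12 offers PWP advice to those randomised. The Section 2 procedures follow a paragraph about follow-up assessments and PWP contacts. The risk protocol, the safety work instruction and the safety flowchart are not shown.

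Much of this stands. The reading that only the outbound SAE process is switched off is possible, and it may be how staff are trained. It is not stated, however, and the plain words go further.

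A reader might also infer that the protocol tells staff to ignore any suicidality before randomisation. The documents do not support that. Thoughts, plans and intent are not SAEs, so the sentence does not touch them, and the closing sentence limits monitoring rather than help during a conversation. The duty in Section 12.4 is weak extra support, since its heading concerns harm to others.

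**Conclusion.** The point holds as a narrow conflict of wording. For a consented, not yet randomised participant who tells staff of a suicide attempt, Section 2 calls for a response and Section 12.3, read literally, says there will be none. This rests on two assumptions: that the unqualified references to participants in Section 2 include people not yet randomised, and that responding keeps its ordinary meaning.

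Severity is low. No event rate is given or derivable, the set-up call is optional, and people who meet the suicidality criterion, which requires recent intention or plans, are excluded at screening. Sample size, estimand and analysis are untouched. It would be wrong to infer that restricting SAE reporting to randomised participants is itself an error.

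**What to change.** In Section 12.3, replace the sentence with text to this effect: *SAEs in non-randomised participants will not be actively sought, recorded or reported. If such a participant discloses risk directly to study staff, the signposting and risk procedures of Section 2 still apply (in the USA, provision of resources and the Coaching Supervisor route), and no SAE form is completed.* In the closing sentence of that paragraph, insert *actively* before the word for monitored.

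The cost is one sentence replaced and one word added. Staff would carry a small load for unsolicited disclosures before randomisation; its size cannot be derived, but it is limited to people who disclose directly to staff. If Section 2 is already meant to cover this period, no new duty arises. The data-minimisation aim is kept, because no SAE data are added.

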12.4. Risk management following notification of potential harm to others

If a participant indicates through any means of communication that they or someone else could be at risk of harm, the study team (typically PWP) will follow a dedicated risk management protocol and may onward report the information to the appropriate authorities, including the police. If this happens, personal identifiable data of the participant and the person at risk of harm may need to be provided to the relevant authority(s). This information will be included in the participant information sheet.

USA-specific detail

Coaches will manage participant risk under supervision of the lead clinical psychologist/site lead.

In the USA, coaches will not make causality assessments. The site lead at UCLA (or clinically qualified delegate) will assess SAEs for causality as soon as practically possible.

[figure not shown]
Participants based in the USA will not be referred on to the equivalent of a GP in the event of an SAE or other adverse event.

If a USA-based participant discloses an SAE to staff, staff will send participants a follow-up survey to ask participants to self-report the details about the reported SAE. If a USA-based participant reports an SAE in their survey responses, they will automatically be presented with additional questions to collect the details of the SAE. This information will then be transcribed into the template SAE form and provided to the site lead for causality assessment. Staff may additionally provide the participant with resources for college, community and emergency services available to them, as appropriate.

As safety data will be entered into the UCLA instance of REDCap, ExeCTU will not have direct access to SAE reports in the database. Therefore, PDF copies of all SAE reports are required to be provided to Exeter Clinical Trials Unit within 24 hours (1 working day) of UCLA team becoming aware of the event.

Figure 2: Safety reporting flowchart

13. STATISTICS AND DATA ANALYSIS

13.1. Target sample size and justification

To detect a Minimum Clinically Important Difference of Standardized Mean Difference (SMD) (Cohen's d) = 0.20 (i.e., a small effect size below which any effect is unlikely to be an important mechanism or specific ingredient) with 90% power at $\alpha=0.05$ in main effect of treatment component(s) requires N=1054 (n=527 per level of each factor). Conservatively estimating 52% dropout attrition posttreatment, we require N≈2192 for Analysis of Variance (or equivalent) to test main effects and two-way interactions. Recruitment rates from our prior online trials confirm this target is feasible.

13.2. Planned recruitment rate

2192 participants over 24 months

13.3. Statistical analysis plan

Analysis will be undertaken in line with the factorial trial extension to the CONSORT agreement for the reporting of trials⁶⁹. Primary inferential analyses, using a treatment policy estimand, will compare the main effects across outcomes using multilevel mixed models adjusting for baseline score, first order interactions, and PWP/coach effect (random effect).

The extent of missing data will be considered and where necessary, in agreement with Trial Steering Committee (TSC), imputation methods will be used (led by co-investigator [name]) to handle missing data whilst minimising bias. These assumptions will further be tested through a sensitivity analyses.

The study statistical analysis plans will be prepared before any formal analyses and reviewed and approved by Data Monitoring and Ethics Committee (DMEC) and TSC. The trial statistician will remain blind to allocation until primary analyses are completed. However, given the complexity of this study and to facilitate communication with the DMEC the senior statistician ([name]) will be unblinded once the Statistical Analysis Plan (SAP) is approved by the DMEC and TSC and has been signed off with the intention that this is achieved prior to the randomisation of the first participant.

13.3.1. Summary of baseline data and flow of patients.

The baseline data being collected in the study is summarised in the Schedule of Events (Table 3). The eCRF for the collection of the baseline data is available as a separate approved document. The baseline data will be collected after the screening and consent, other than those items listed under the 'eligibility screen' heading which will be collected as part of the screening survey. The measures are detailed fully in separately approved assessment documents for the various timepoints. The flow of patients throughout the study is outlined in Figure 1.

13.3.2. Primary outcome analysis

The primary analysis will investigate the between factors difference change in RNT from baseline to post-treatment (16 weeks). The primary outcome will be reported descriptively (mean and standard deviations (SD)) and inferential comparisons will be reported between the levels of the treatment factors (High versus Low levels in Be specific, Break Habit, Be Kind, Be present) adjusting for the first order interactions.

All analysis will be based on a treatment policy estimand and will include participants with primary outcome data at 16 weeks, we will adjust for the stratification variables (location (UK or USA), caseness or not for anxiety or depression) and if necessary adjust for any significant imbalance in baseline participant characteristics (if there is >1SD difference in mean or >10 percentage points for categorical data and the variable is thought to be predictive of outcome).

Analysis will be using an adjusted multilevel mixed model to investigate the effect of the four treatment factors and their first order interactions.

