13.5. Participant analysis population(s)

Analysis will be undertaken on three participant populations:

- **All-randomised population:** Any participant randomised into the study, regardless of whether they received study treatment (intention-to-treat)
- **All-treated population:** Any participant randomised into the study that received any amount of study treatment
- **Protocol-compliant population:** Any participant who was randomised and received the protocol required treatment exposure and required protocol processing

With the primary analysis based on a treatment policy estimand and therefore based on the all-randomised population. The results of the analysis on the all-treatment and protocol compliant populations will be used to provide insight related to the primary analysis.

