13.6. Procedure(s) to account for missing or spurious data

The data will be collected and stored to both highlight and minimise the chances of missing or spurious data. Patterns of missing outcome data at follow-up will be extensively investigated. Imputation models will be used to impute missing primary and secondary outcome data and any explanatory variables at all follow-up time points. Results for the between group comparisons based on these imputed data sets will be presented in addition to the primary analysis described. Propensity for missingness and potentially spurious values associated with baseline characteristics will be investigated; imputation models will include treatment allocation as well as stratification variables, baseline variables, and any variables associated with missingness or included in the models as covariates due to baseline imbalance. The potential for introducing bias through the imputation of missing data will be extensively considered and where appropriate highlighted.

13.7. Other statistical considerations.

No formal p-value adjustment will be made for multiple testing; the results of the treatment policy estimand analyses will be interpreted first, and the results of the additional analyses interpreted in this light. The focus of the analysis will be on the four treatment factor comparisons. However, the first order interactions will also be investigated and reported on. Interpretation of results will draw focus on confidence intervals rather than emphasising p-values.

Given the complexity of the study the lead statistician will be unblinded following the sign-off of the statistical analysis plan. However, the primary analyses will be performed by a statistician who remains blinded to group allocation and will be presented as such to the investigators. The results will be discussed and interpreted prior to the unblinding of group allocations. Additional analyses will then be performed following unmasking.

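### The primary analysis set is stated two ways: Sections 13.3.2 and 13.3.5 keep only participants with 16-week data, while Section 13.5 says all randomised; followed as written, an observed-case result would carry an all-randomised label

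*Protocol*

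**What the plan says.** Five places in the Protocol bear on who is in the primary 16-week comparison.

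- **13.3.2 Primary outcome analysis:** "All analysis will be based on a treatment policy estimand and will include participants with primary outcome data at 16 weeks". Section 13.3.5 (Adjusted analysis) repeats the clause.
- **13.5 Participant analysis population(s):** "With the primary analysis based on a treatment policy estimand and therefore based on the all-randomised population". That population is defined as anyone randomised, whether or not they received treatment, and is glossed as intention-to-treat. Nothing in the definition requires an outcome.
- **13.6 Missing or spurious data:** imputation models will be used for the primary outcome, but "Results for the between group comparisons based on these imputed data sets will be presented in addition to the primary analysis described".
- **13.3 Statistical analysis plan:** imputation is conditional, to be used where needed and with the Trial Steering Committee's agreement.
- **13.1 Sample size:** the calculation "requires N=1054 (n=527 per level of each factor", and then, "Conservatively estimating 52% dropout attrition posttreatment", inflates this to about 2,192 randomised.

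The model in 13.3 and 13.3.2 is a multilevel model of the 16-week PTQ change, adjusted for baseline score, stratification variables and first-order interactions, with PWP/coach as a random effect.

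**The concern.** The same estimand is used to justify two different analysis sets. One is conditional on having a 16-week score; the other is not. No section reconciles them.

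The rest of the text shows which would apply in practice. The model as described takes one post-baseline PTQ per person, and its random effect is for PWP/coach, not for repeated measures within a participant. Someone without a 16-week score contributes nothing to it. Imputation could bring such people in, but 13.6 places it outside the primary analysis. The primary result would therefore be an observed-case result that 13.5 labels all-randomised.

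This affects the main result for all four factors, and Section 13.7 says the treatment-policy results are interpreted first, with other analyses read in their light. A reader would take the result to describe everyone randomised when about half may be absent. While both statements stand, the set could also be chosen after the data are seen.

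**Working it through.** **1. The protocol's own figures.** Inputs from 13.1: SMD 0.20 (so SD = 1), 90% power, alpha 0.05 (sidedness not stated; two-sided assumed), 52% attrition.

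- Per level, normal approximation: 2 × (1.960 + 1.282)² / 0.20² ≈ 525.4, so 526 (1,052 in total). The exact t calculation gives 527 (1,054), the stated figure.
- Inflation: 1,052 / 0.48 = 2,192; 1,054 / 0.48 = 2,196. The stated 2,192 is reproduced.

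The plan is thus sized on participants with outcomes, which matches 13.3.2 and not 13.5.

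**2. How many people the two definitions separate.** Omitted = 2,192 × attrition.

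| Attrition | Kept under 13.3.2 | Omitted | Kept under 13.5 |
|---|---|---|---|
| 20% | 1,754 | 438 | 2,192 |
| 30% | 1,534 | 658 | 2,192 |
| 40% | 1,315 | 877 | 2,192 |
| 52% (planned) | 1,052 | 1,140 | 2,192 |

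Power for 0.20 SD with 1,052 people is 90.0%. The issue is who is represented and possible bias, not lost power.

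**3. Whether the omission can bias the contrast.** The protocol gives no data on this, so the check is a simulation with assumed inputs: true reduction 0.20 SD; 52% lost at each level of a factor; the log-odds of dropout rise with early RNT; correlations between measures of roughly 0.6 to 0.75; at least 200,000 simulated people per scenario. For the PTQ-only mixed model, 0% to 50% of those missing week 16 were assumed to return at week 52. Ranges cover the assumed values.

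| Dropout slope per SD (high level / low level) | Observed-case ANCOVA | Mixed model, PTQ at 0, 16, 52 weeks only | All randomised, also using early RNT |
|---|---|---|---|
| Equal (0.5/0.5 or 1.0/1.0) | 0.197 to 0.207 | – | about 0.20 |
| 1.0 / 0.5 | 0.28 to 0.29 | 0.265 to 0.286 | about 0.20 to 0.21 |
| 0.5 / 1.0 | 0.11 to 0.12 | 0.12 to 0.14 | about 0.20 to 0.21 |

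Taking one run: 0.282 − 0.200 = 0.082 and 0.200 − 0.116 = 0.084. Each, divided by 0.20, is 41% to 42%, or about 40% of the target difference.

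**4. Why the PTQ-only model does not help.** The variable driving dropout in this scenario is RNT during treatment. A participant with only a baseline PTQ adds almost nothing to the week-16 contrast, and a week-52 score for some of the missing recovers little. Information on early RNT is needed. Section 8.5.1 already collects it: brief RNT measures in the micro-assessments at weeks 1 to 5, 7, 9, 11, 13 and 15.

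**The case against.** The best defence is that the two sections answer different questions. Section 13.5 separates populations by treatment received, and 13.3.2 says who has an outcome; together they would mean analysed as randomised, among those with data. Treatment policy deals with intercurrent events such as stopping the intervention and does not fix a missing-data method. That last point is right, but it also means the estimand cannot justify dropping people without outcomes. And 13.5 says the analysis itself, not just the target, is based on all randomised, with no condition on observed data. The reconciling sentence is absent.

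Second, missing data are not ignored. Section 13.6 commits to imputing the primary outcome, studying missingness and presenting the imputed results. This stands: an all-randomised result should be reported. A reader might infer that non-responders are never accounted for; the document does not support that. The defect is that the imputed result is not the primary one, and that 13.3 makes imputation conditional where 13.6 does not.

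Third, the size. The protocol calls 52% conservative, and Section 8.5.2 allows the primary outcome to be collected by telephone, so fewer than 1,140 may be missing. No passage suggests that dropout depends on RNT differently by factor level, and every variant has the same core content and PWP/coach support. Participants are unblinded and the factors change the content they receive, so a difference is plausible, but it is not shown.

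**Conclusion.** The inconsistency is real, lies in the current text, and does not depend on an unseen statistical analysis plan. Followed as written, the primary result is an observed-case analysis described as all-randomised. The number left out is about 1,140 of 2,192 at the planning attrition and 658 at 30%.

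Two stronger readings should be resisted. One is that the primary result will be biased by 40% of the 0.20 target. That figure rests on an assumed two-fold difference in dropout slope between levels; with equal slopes the observed-case estimate is nearly unbiased. The documents establish that the analysis is exposed to such bias, not that it will occur. The other is that any all-randomised mixed model removes the problem. A model on PTQ at baseline, 16 and 52 weeks alone would satisfy 13.5 in name and leave nearly all of the error in this scenario.

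The recommended method rests on missingness at random given the data used. Micro-assessments begin only once the participant reinstalls the m-Path app, so those who never do so will have no early RNT data, and for them that assumption is at its weakest.

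**What to change.** Amend 13.3, 13.3.2, 13.3.5, 13.5 and 13.6 together; changing only 13.3.2 and 13.5 would leave the repeated clause in 13.3.5 and the conditional imputation in 13.3.

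- State one primary set: all randomised participants.
- Name one primary method, likelihood-based or multiple imputation, and state its missing-at-random assumption.
- Have that method use the RNT micro-assessments from weeks 1 to 15 as well as PTQ at baseline, 16 and 52 weeks, with the factor contrasts read at week 16.
- Report the analysis of participants with 16-week data as a labelled sensitivity analysis.
- Make 13.6 consistent, so that the chosen method is part of the primary analysis and not an addition to it.

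The cost is protocol and statistical analysis plan wording and a somewhat more complex primary model. No new data are needed.
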